4.3 PE parameters for secondary analyses of prevention efficacy

Secondary analyses assess PE parameters for the mAb dose groups separately. Let PE10 be the overall PE of the 10 mg/kg mAb group and let PE30 be the overall PE of the 30 mg/kg mAb group, defined as

 $PE10 = [1 - Cumul. incid. ratio (mAb-10 mg/kg grp/control) of HIV-1 Dx by 80 Wks] \times 100\%$

and

 $PE30 = [1 - Cumul. incid. ratio (mAb-30 mg/kg grp/control) of HIV-1 Dx by 80 Wks] \times 100\%$.

Secondary analyses test the null hypotheses

H0: PE10 = 0% versus the alternative hypothesis H1: PE10 \neq 0%

and

H0: PE30 = 0% versus the alternative hypothesis H1: PE30 \neq 0%

using 2-sided alpha = 0.05 level tests. Both unadjusted p-values and Holm-Bonferroni p-values will be reported for each of the individual dose versus placebo group analyses.

In addition, the following secondary analyses of PE are conducted:

• Assess a dose-response effect by testing the null hypothesis

H0: Cumul. HIV-1 incidence by 80 Wks equal in the 3 groups versus H1: $0\% \le PE10 \le PE30$ with at least one strict inequality

- Test the complete null hypothesis that the HIV-1 incidence is the same in the three treatment groups versus the alternative hypothesis that there are some differences
- Test for different HIV-1 incidence between the two mAb groups, where a finding of PE30 significantly greater than PE10 would demonstrate that assignment to a higher mAb dose level causes higher PE

4.4 Statistical rationale for the 3-arm design compared to a 2-arm design

An alternative design would compare a single dose and schedule of the VRC01 mAb versus control. However, the 3-arm design allows addressing additional scientific questions and improves the assessment of correlates of protection, without requiring more participants by virtue of the primary analysis being based on the pooled mAb groups versus control. Specifically, consider a 2-arm design with 2:1 allocation to a single dose of VRC01 versus placebo, compared to the 3-arm design in the protocol with 1:1:1 allocation. For scenarios where the average of PE10 and PE30 equal PE set to a number greater than 0 and less than 1, power to reject H0: PE $\leq 0\%$ in favor or H1: PE > 0% is very similar between the two trial designs, for the same total number of study participants. By providing results about estimated PE10 and estimated PE30 as well as about pooled estimated PE, the trial provides data for modeling of how PE would change given a new dose and/or schedule.

A second advantage of the 3-arm design is that it allows a direct assessment of the causal effect of different mAb infusion doses on HIV-1 incidence based on randomization of treatment assignments (a so-called 'group-level' correlate of protection), which can directly prove the concept that a higher mAb dose causes a greater level of protection. In contrast, with a 2-arm design the association between mAb marker characteristics and the level of PE can only be inferred with non-randomized epidemiological analysis approaches for which the results cannot be guaranteed to be free from postrandomization selection bias [112,113]. That is, without a randomization to multiple mAb interventions a result that a mAb characteristic is associated with reduced incidence of HIV-1 infection may not imply that mAb recipients with the characteristic have a higher level of PE. For instance, the implication may fail if participants tend to have fewer HIV-1 exposures during the few weeks after infusion visits compared to during the few weeks before infusion visits, which could possibly occur related to the counseling and informed consent process. Or, the implication may fail if the mAb characteristic marks an intrinsic

HIV-1 susceptibility factor that is not caused by administration of the mAb [114-116]. A third advantage of the 3-arm design is that the random assignment of two mAb doses creates greater inter-individual variability in mAb characteristics, which improves statistical power for the assessment of individual-level correlates of protection.

In sum, the dose-response 3-arm design has the advantages of allowing more insightful and rigorous inferences about causal effects of the mAb and greater resolution of correlates of protection, and allows addressing the additional question of whether a higher dose confers greater PE than a lower dose.

4.5 Use of safety run-in data in the analyses of prevention efficacy

Data from all participants, irrespective of enrollment into the safety run-in cohort, are included in analyses of prevention efficacy. This is valid because all enrolled participants have the same schedule for infusions and follow-up. In the event that infusions are paused, the analysis plan would be amended to censor participant follow-up more than approximately 10 weeks beyond the last infusion after the pause is instituted.

4.6 Sample size calculations for testing for overall PE (Primary objective 2)

The trial is designed to have 90% power to test

H0: $PE \le 0\%$ versus the alternative hypothesis H1: PE > 0%

if the level of overall pooled PE is 60% (with a 1-sided 0.025 α -level test); the design fits the paradigm of an intermediate-sized phase 2b screening efficacy trial proposed for HIV-1 vaccine efficacy trials by Rida, Fleming et al [117].

The sample size calculations are based on the power of a 1-sided 0.025-level Wald test for comparing log-transformed cumulative incidences of HIV-1 infection by the Week 80 visit between randomized groups, in the presence of the sequential monitoring described below. Power is computed based on simulating 10,000 efficacy trials under assumptions described below using the R package seqDesign.

4.6.1 Assumptions of the sample size calculations including sequential monitoring for PE

The following assumptions are made for the sample size calculations:

- 10% annual dropout incidence in each of the three study groups
- 32 month uniform accrual with halved accrual during the first three months (approximating current accrual projections)
- visits every 4 weeks for HIV-1 diagnostic tests through Week 80 and HIV-1 status at Week 80 is known
- 3% annual HIV-1 incidence in the control group

- For each of the mAb treatment groups, average PE versus control within an 8-week infusion interval is assumed to be the same for each of the 10 infusion intervals
- Sequential monitoring of the mAb groups versus control to stop early for:
 - Potential harm [Establish that PE (pooled over the mAb groups) < 0% based on a 2-sided monitoring adjusted 90% CI lying below 0%]
 - Non-efficacy [Establish that PE (pooled over the mAb groups) $\leq 40\%$ based on a 2-sided 95% nominal CI lying below 40%]
 - High efficacy [Establish that PE (pooled over the mAb groups) > 70% based on a 2-sided 95% nominal CI lying above 70%]

With the exception of the potential harm monitoring, the sequential monitoring of PE does not use critical values adjusted for the number of analyses. Examination of the design operating characteristics (reported in the figures and tables below) was used to ensure that this approach provides a fitting trade-off of the control of false negative and false positive error rates.

Justification for the incidence assumptions is provided in Section 4.6.6.

We also show power calculations allowing for lower levels of HIV-1 incidence or higher levels of dropout. In particular, we show power calculations assuming 1.65% annual HIV-1 incidence in the control group, which would account for lower than expected incidence rates due to increased PrEP usage. Similarly, power calculations based on 15% annual dropout incidence are also considered.

4.6.2 Power curves and operating characteristics of the design (Primary objective 2)

Required sample sizes to achieve 90% power to reject H0: $PE \le 0\%$ in favor of H1: PE > 0% for different values of PE are determined based on 1-sided 0.025 level Wald tests as described above. The power calculations are repeated for a range of sample sizes to determine the required sample size to achieve 90% power as reported in Figure 4-1. These power calculations are conducted using the open source R package seqDesign developed by the protocol statisticians [118], which computes power based on simulating many thousands of efficacy trials, applying the sequential monitoring procedures to each trial, and computing power as the fraction of the trials where the 1-sided 0.025-level Wald test rejects the null hypothesis. The calculations are based on a large number of simulated efficacy trials.

Figure 4-1 shows the sample size per group in the three treatment groups required to have 90% power to reject H0: $PE \le 0\%$ in favor of H1: PE > 0% for different values of PE = PE10 = PE30. The results show that about N = 2300 total participants are needed to achieve 90% power to detect PE = 60%; the sample size N = 2700 total participants (900 per arm) is selected to build in a provision of robustness to the control group annual incidence being lower than 3.0%. In particular, the lowest control group annual HIV-1 incidence to retain power of at least 90% to detect PE = 60% is 2.3%.

[figure not shown]

Figure 4-1 Total sample size for 90% power to reject H0: $PE \le 0\%$ in favor of H1: PE > 0% in a 1:1:1 allocation design with 80 weeks of follow-up for HIV-1 infection for each trial participant

Table 4-1 shows power available to reject the null hypothesis under different levels of true PE.

Table 4-1 Power for rejecting H0: $PE \le 0\%$ in favor of H1: $PE > 0\%$ under different effect sizes
PE = PE10 = PE30

	Unconditional Power (× 100)		
0%	2.4		
10%	7.8		
20%	19.0		
30%	38.6		
40%	62.9		
50%	84.2		
60%	96.0		
70%	99.5		
80%	>99.9		
90%	>99.9		
95%	>99.9		

The power calculations for the primary analysis of prevention efficacy were done assuming PE10 = PE30, and it is of importance to also understand power available in the primary analysis in the event that PE10 differs from PE30. Power for rejecting H0: $PE \le 0\%$ in favor of H1: PE > 0% when PE equals a fixed constant PE₀ greater than 0 and less than 1 is very similar for different values of (PE10, PE30) subject to the constraint of average value (PE10+PE30)/2 = PE₀. For example, power to test H0 vs. H1 is very similar for (PE10, PE30) = (60\%, 60\%) and for (PE10, PE30) = (30\%, 90\%). This result attains because all of these scenarios have the same number of expected HIV-1 infection events among study participants assigned to receive VRC01. Power tends to be slightly greater for differential scenarios like (PE10, PE30) = (30\%, 90\%) compared to the equal scenario (PE10, PE30) = (60\%, 60\%), because the hypothesis testing procedure stratifies by VRC01 dose group, gaining efficiency by accounting for a baseline variable that predicts HIV infection. Therefore, the trial is powered to detect the design alternative of a dose-pooled VRC01 efficacy PE equal to 60%, regardless of whether VRC01 efficacy differs by dose group.

4.6.3 Additional operating characteristics of the design for assessing primary objective 2

For the selected sample size (N = 2700), Figure 4-2 shows the power curves for rejecting H0: $PE \le 0\%$ in favor of H0: PE > 0% for a range of fixed values of the pooled PE. The power for rejecting H0 when the HIV-1 incidence rate is lower than projected or dropout rate is higher than projected are included in the figure.

The scenario of 1.65% annual HIV-1 incidence represents various amounts of PrEP use among study participants. In particular, this 1.65% assumption is attained if 50% of person-years at–risk are not during PrEP use with annual incidence of 3.0%, and the other 50% of person-years at-risk are during PrEP use at PrEP efficacy of 90% and hence with annual incidence of 0.3% [1.65% = (3.0% + 0.3%)/2]. In addition, a slightly higher control group annual incidence of 2.0% is attained under each of the following three scenarios, all of which assume 90% PrEP efficacy during PrEP use and 3% annual HIV-1 incidence during person-years at-risk without PrEP use: (A) 50% of person-years at-risk during PrEP use in the U.S. and Switzerland; 25% in Peru and Brazil; and 69% participants enrolled in the U.S. and Switzerland; (B) 60% of person-years at–risk during PrEP use in the U.S., 30% in Peru and Brazil, and 61% of participants enrolled in the U.S. and Switzerland; (C) 75% of person-years at–risk during PrEP use in the U.S. and Switzerland, 40% in Peru and Brazil, and 48% of participants enrolled in the U.S. and Switzerland. These calculations support that the study has adequate power to meet the primary efficacy objective if there is substantial PrEP use.

Moreover, we also conducted power calculations assuming 50% of person-years at-risk during PrEP use in all three countries, which means that the overall annual HIV-1 incidence in the placebo group is 1.65% [= (3.0% + 0.3%)/2]. In this scenario, the trial has 78% power to detect PE = 60%.

[figure not shown]

Figure 4-2 Unconditional power to reject H0: $PE \le 0\%$ in favor of H1: PE > 0% for a range of fixed values of pooled PE based on primary assumptions for HIV-1 incidence and dropout rate. Power curves are also shown for a lower than expected HIV-1 incidence rate and a higher than expected dropout rate.

4.6.4 Additional operating characteristics of the primary analysis accounting for the sequential monitoring

For the selected sample size (N = 2700), Figure 4-3 shows probabilities of reaching each possible trial monitoring outcome, pooling over the two mAb treatments (under the primary assumptions about HIV-1 incidence and dropout rates). More specifically, the monitoring outcomes include potential harm, non-efficacy, and high efficacy. Table 4-2 provides the same information in tabular form. In addition, the figure and table show unconditional power in the primary analysis to reject the null hypothesis H0: $PE \le 0\%$ in favor of the alternative hypothesis H1: PE > 0%.

[figure not shown]

Figure 4-3 Probabilities of reaching each possible trial monitoring outcome, and unconditional power to reject the primary null hypothesis H0: PE ≤ 0%with 900 control recipients and 1800 mAb recipients (1-sided 0.025-level tests)

		Weed Out at Int	erim Analysis		
		Potential Harm	Non-Efficacy	High Efficacy	Unconditional Power
PE	HR	PE < 0%	PE < 40%	PE > 70%	PE > 0%
	3.0	95.3	4.7	0.0	0.0
	2.5	87.8	12.2	0.0	0.0
	2.0	69.1	30.9	0.0	0.0
	1.5	34.0	66.0	0.0	0.0
0%	1.0	4.9	92.7	0.0	2.4
10%	0.9	2.6	89.6	0.0	7.8
20%	0.8	1.1	79.8	0.0	19.0
30%	0.7	0.4	61.0	0.0	38.6
40%	0.6	0.1	37.0	0.0	62.9
50%	0.5	0.0	15.8	0.0	84.2
60%	0.4	0.0	4.0	0.1	96.0
70%	0.3	0.0	0.5	2.0	99.5
80%	0.2	0.0	0.0	23.6	100.0
90%	0.1	0.0	0.0	85.4	100.0
95%	0.0	0.0	0.0	99.2	100.0

Table 4-2 Probabilities (x 100) of reaching each possible trial monitoring outcome, and unconditional power (x 100) to reject the null hypothesis H0: $PE \le 0\%$ in favor of the alternative hypothesis H1: PE > 0%, pooling over the two mAb groups (1-sided 0.025-level tests)

N = 900:1800 Control:mAb group 3% annual incidence in the Control group

10% annual dropout

Cumulative incidence-based non-efficacy monitoring

Cumulative incidence-based high-efficacy monitoring

Cumulative incidence-based unconditional power

Table 4-3 shows the numbers of HIV-1 infection endpoints during the trial expected under the null hypothesis scenario PE = PE10 = PE30 = 0% and under the design

alternative hypothesis scenario PE = PE10 = PE30 = 60%. Under the design alternative hypothesis scenario, the calculations show that 37 HIV-1 infection endpoints are expected in the control group and 30 HIV-1 infection endpoints are expected in the two mAb groups combined after 80 weeks of follow-up.

Table 4-3 Cumulative number of HIV-1 infection endpoints over 80 weeks of follow-up under
the null hypothesis scenario PE10 = PE30 = 0% and under the design alternative hypothesis
scenario PE = PE10 = PE30 = 60%. Medians are computed based on simulating a large
number of efficacy trials.

PE10 = PE30	Weeks since first person in	Median number of control endpoints	Median number of pooled mAb group endpoints
0%	0	0	0
0%	26	0	1
0%	52	3	7
0%	78	9	18
0%	104	16	32
0%	130	22	45
0%	156	25	50
0%	182	26	54
0%	208	26	55
0%	210	26	55
60%	0	0	0
60%	26	0	0
60%	52	3	3
60%	78	9	7
60%	104	16	13
60%	130	23	19
60%	156	30	24
60%	182	35	28
60%	208	37	30
60%	219	37	30

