4.9.1.1 Sequential monitoring for potential harm, non-efficacy, and high efficacy

The trial uses sequential monitoring of the mAb groups versus control to stop early for:

- Potential harm [Establish that PE (pooled over the mAb groups) < 0% based on a 2-sided monitoring-adjusted 90% CI lying below 0%]
- Non-efficacy [Establish that PE (pooled over the mAb groups) < 40% based on a 2-sided 95% nominal CI lying below 40%]
- High efficacy [Establish that PE (pooled over the mAb groups) > 70% based on a 2-sided 95% nominal CI lying above 70%]

The sequential monitoring is based on CIs in order that the result of the study that would be reported would convey evidence supporting the conclusion of potential harm, non-efficacy, or high efficacy. Freidlin, Korn, and Gray [120] discuss a rationale for this approach to non-efficacy monitoring. The sequential monitoring for potential harm is based on monitoring-adjusted 1-sided 0.05-level tests (instead of 1-sided 0.025-level tests) for prudence to protect the safety of study participants (ie, less precision is required to meet a guideline for potential harm than to meet guidelines for non-efficacy or high-efficacy). Once non-efficacy monitoring commences, the potential harm monitoring after each infection ceases, as the non-efficacy monitoring now provides the function of detecting an elevated rate of HIV-1 infection. The non-efficacy monitoring is supplemented with conditional power calculations that report estimates of the probability of rejecting the null hypothesis of zero PE under different assumptions about the estimated PE if the trial were to continue to the end. The sequential monitoring plan is summarized in Table 4-6 and Figure 4-7.

Monitoring Type	Hypotheses	Testing Approach	Size of Test	Stopping Boundary	Timing of Interim Analyses
Potential Harm	H0: PE ≥ 0% vs H1: PE < 0%	Exact 1-sided binomial test of the fraction of infections assigned to receive the mAb	Specified in the monitoring plan	Near-constant 1-sided p- value cut-off controlling the FWER at α = 0.05*	After every infection from 20 th total until first non- efficacy analysis
Non- Efficacy	H0: PE ≥ 40% vs H1: PE < 40%	2-sided Wald test and 1:1 corresponding 2- sided 95% Cl	1-sided α = 0.025	Nominal 2-sided 95% Cl below 40% supplemented with conditional power (specified in the monitoring plan)	6-monthly starting based on an event- driven trigger specified in the monitoring plan

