## 9.2 Sequential Monitoring of Prevention Efficacy for Potential Harm, Non-Efficacy, and High Efficacy

For each trial, PE is monitored by the independent DSMB at each DSMB meeting, with triggers based on numbers of primary HIV-1 infection endpoints for when the DSMB meetings begin to include formal evaluation of the potential harm, non-efficacy, and high efficacy stopping boundaries (these triggers are described below). The approach to sequential monitoring of PE is similar to that described in Gilbert, Grove et al. (2011). The monitoring of PE in the AMP trials is also similar to that used for the HVTN 505 phase 2b HIV-1 vaccine efficacy trial (Hammer et al., 2013). Each of the AMP trials uses sequential monitoring of the pooled mAb groups versus control to stop early for:

- potential harm [establish that PE (pooled over the mAb groups)  $< 0\%$  based on a 2-sided monitoring-adjusted 90% confidence interval lying below 0%]
- non-efficacy [establish that PE (pooled over the mAb groups)  $< 40\%$  based on a 2-sided 95% nominal confidence interval lying below 40%]

Table 3: Summary of sequential monitoring of PE for each AMP trial

Monitoring Type	Hypotheses	Testing Approach	Size/Power	Monitoring Plan	Number of Interim Analyses
Potential Harm	$H_0 : PE \geq 0\%$ vs. $H_1 : PE < 0\%$	Exact 1-sided binomial test of the proportion of infections assigned to a mAb group	1-sided $\alpha = 0.05$	Near-constant* 1-sided p-value cut-off controlling the FWER at $\alpha = 0.05$	After every infection from 20 th total until first non-efficacy analysis
Non-Efficacy	$H_0 : PE \geq 40\%$ vs. $H_1 : PE < 40\%$	Wald test	1-sided $\alpha = 0.025$	Nominal 2-sided 95% CI supplemented with conditional power	6-monthly starting after at least 45 but no more than 67 total infections †
High Efficacy	$H_0 : PE \leq 70\%$ vs. $H_1 : PE > 70\%$	Wald test	1-sided $\alpha = 0.025$	Nominal 2-sided 95% CI	6-monthly starting at the same time as for non-efficacy

\*An increasing per-test alpha until a constant level is reached that, if applied to all subsequent tests, maintains the specified FWER

†The first non-efficacy/high efficacy interim analysis occurs either at the scheduled DSMB meeting at which there are 45 or more primary endpoint events across the three study groups or when 67 total primary endpoint events are observed, whichever occurs earlier.

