### 9.2.2 Non-efficacy monitoring

For each AMP trial, the first non-efficacy analysis will be reported to the DSMB at the first scheduled 6-monthly meeting at which at least a total of 45 HIV-1 infection endpoints have occurred, combined over the three study groups. The analysis is based on all HIV-1 infection endpoints up until the time of data lock, and if this number exceeds 67, then the first non-efficacy analysis would be done based on 67 events and the report provided to the

DSMB by secure means prior to the scheduled DSMB meeting (as noted above).

At each non-efficacy interim analysis PE is estimated with a 2-sided 95% nominal confidence interval using the same method as for the final analysis of PE described in Section 8.1. Cumulative prevention efficacy through time  $t$ ,  $PE(t)$ , will be estimated at time point  $t$  chosen to be the latest possible time point when stable estimation with follow-up data through the Week 80 visit (or earlier if necessary) can be achieved; this is operationalized by defining  $t$  as the maximum time point when 150 participants are observed to be at risk for the primary endpoint in each of the placebo and pooled VRC01 groups. The timepoint  $t$  will be chosen for evaluation of whether the stopping boundary is crossed or not. All times-to-event will be right-censored at the Week 80 visit or earlier following the operational rules summarized in Table 1. As stated in Table 3, the non-efficacy stopping boundary is defined by the 2-sided upper 95% confidence limit for PE being at 40%, where the 95% CI lying below 40% with the lower 95% confidence limit lying below 0% constitutes meeting the guideline for non-efficacy.

The 2-sided 95% confidence intervals for PE, estimated in the same way as described for the final analysis, are reported for sequential monitoring of PE at every DSMB meeting through to the end of the trial.

In addition, a supplemental analysis will estimate the proportional-hazards PE parameter (defined in (3)) with a 2-sided 95% confidence interval and a two-sided p-value for whether proportional-hazards PE differs from unity, following the same statistical procedures described for the final analysis plan (see Section 8.2).

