#### **9.2.4 Rationale for starting non-efficacy/high efficacy monitoring at at least 45 total infections**

Freidlin, Korn, and Gray (2010) suggested beginning non-efficacy monitoring as soon as a point estimate of PE equal to zero would correspond to the nominal 95% confidence interval of a hazard ratio based efficacy parameter under a Cox proportional hazards model just barely ruling out the design alternative (PE = 40% in the AMP trials). This approach implies starting the non-efficacy monitoring at the 67th total infection in each AMP trial. However, based on protocol projections of accrual and incidence, between about 60 and 100 total HIV-1 infection events are expected in each trial, for PE varying over the range 0% to 60%. Therefore it would not be unlikely that no non-efficacy interim analysis would occur if the Freidlin, Korn, and Gray (2010) recommendation were strictly followed. Moreover, a high efficacy analysis would not occur, as its timing is synchronized to the non-efficacy monitoring timing, which could be problematic if the PE is very high. Accordingly, the monitoring starts at at least 45 infections, which is judged to be large enough to have reasonable precision and small enough to make it likely that some non-efficacy/high efficacy interim analyses would occur during the trial. Note that if the first non-efficacy interim analysis occurred at 45 total infections, then stopping for non-efficacy, which would occur if the nominal 2-sided 95% confidence interval lies below 40%, would correspond to a negative PE estimate. This is an advantageous property in that a result of early non-efficacy would be an unambiguous result about absence of prevention efficacy.

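### Protocol Table 4-2 counts trials that finish without rejecting the null as interim non-efficacy stops (37.0% printed at PE 40%; about 4–8% under the stated rule)

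*Protocol*

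**What the plan says.** Protocol Section 4.6.4 introduces Figure 4-3 and Table 4-2 as the probabilities of the monitoring outcomes: "More specifically, the monitoring outcomes include potential harm, non-efficacy, and high efficacy. Table 4-2 provides the same information in tabular form". The table caption is "Probabilities (x 100) of reaching each possible trial monitoring outcome, and unconditional power (x 100) to reject the null hypothesis". In the table, Non-Efficacy carries the sub-heading PE < 40% and stands under a spanning header about weeding out at an interim analysis.

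Sections 4.6.1 and 4.9.1.1 define non-efficacy by one criterion: "Establish that PE (pooled over the mAb groups) < 40% based on a 2-sided 95% nominal CI lying below 40" percent. SAP Section 9.2, Table 3, sets the timing as "6-monthly starting after at least 45 but no more than 67 total infections". SAP Section 9.2.2 adds a clause on the lower limit: "the 95% CI lying below 40% with the lower 95% confidence limit lying below 0% constitutes meeting the guideline for non-efficacy". The protocol leaves the start trigger to a separate monitoring plan.

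Section 4.6.1 relies on the results to justify unadjusted critical values: "Examination of the design operating characteristics (reported in the figures and tables below) was used to ensure that this approach provides a fitting trade-off". No text or footnote says that the non-efficacy column also includes trials that end without rejecting the null.

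**The concern.** A trial can pass all its interim looks, finish, fail to reject PE ≤ 0%, and still have a CI that includes 40%. That trial meets neither the non-efficacy rule nor the efficacy criterion. At moderate PE it should be a common outcome, yet Table 4-2 leaves no probability for it.

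Read as printed, the table says that an ineffective product is weeded out early in 93% of trials and that a 40%-effective product is stopped for non-efficacy in 37%. A DSMB or funder would conclude that the rule is quick to stop a useless product and harsh on a moderately effective one. The risk of a completed but inconclusive trial cannot be read from the table at all.

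**Working it through.** **1. Row sums of Table 4-2 (harm + non-efficacy + power).** Examples: PE 0%: 4.9 + 92.7 + 2.4 = 100.0. PE 20%: 1.1 + 79.8 + 19.0 = 99.9. PE 40%: 0.1 + 37.0 + 62.9 = 100.0. PE 60%: 0.0 + 4.0 + 96.0 = 100.0. HR 1.5: 34.0 + 66.0 + 0.0 = 100.0. Fourteen of the 15 rows give 100.0 and the other gives 99.9.

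**2. Closed-form check on full data, without monitoring.** Inputs from Section 4.6.1 and the table notes: "N = 900:1800 Control:mAb group 3% annual incidence in the Control group", 10% annual dropout, 80 weeks of follow-up. With infection rate λ, dropout rate d = 0.10 and τ = 80/52, expected events are n·λ·(1 − exp(−(λ + d)τ))/(λ + d).

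- Control: 900 × 0.03 × (1 − exp(−0.13 × 80/52))/0.13 = 37.6. Table 4-3 gives a median of 37 under PE 60%.
- SE of the log ratio = √(1/d_c + 1/d_m), where d_c and d_m are control and pooled mAb events.
- Power = Φ(−ln HR/SE − 1.96).
- P(95% CI below 40%) = Φ((ln HR − ln 0.6)/SE − 1.96).

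For PE 40%: d_m = 45.6 and SE = √(1/37.6 + 1/45.6) = 0.220. Power = Φ(0.511/0.220 − 1.96) = 64.0%, and P(CI below 40%) = Φ(−1.96) = 2.5%.

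| PE | mAb events | Power (printed) | P(CI < 40%) | Printed non-efficacy | 100 − power | Printed harm + non-efficacy |
|---|---|---|---|---|---|---|
| 0% | 75.3 | 2.5 (2.4) | 72.5 | 92.7 | 97.5 | 97.6 |
| 20% | 60.5 | 18.8 (19.0) | 28.3 | 79.8 | 81.2 | 80.9 |
| 40% | 45.6 | 64.0 (62.9) | 2.5 | 37.0 | 36.0 | 37.1 |
| 60% | 30.5 | 96.4 (96.0) | 0.0 | 4.0 | 3.6 | 4.0 |

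The power column is reproduced. The non-efficacy column tracks failure to reject, not the CI rule.

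**3. A bound that needs no start trigger.** At a true PE of 40% the nominal CI lies below 40% in about 2.5% of trials at any one look. Table 4-3 ends at week 219, and 219/26 = 8.4, so there are at most 8 six-monthly looks. The interim stopping probability is then at most about 8 × 2.5% = 20%. The table prints 37.0.

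**4. Trial simulation (20,000 trials per row).** Settings: 32-month accrual at half rate for the first three months, 4-weekly diagnosis, 10% dropout and the SAP harm boundary. The CI is a Nelson-Aalen log cumulative-incidence-ratio CI at the latest time with 150 at risk per group. Looks are 6-monthly from 45 infections (cap 67), followed by a final one-sided 0.025 Wald test.

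| PE | Power (printed) | Interim non-efficacy | Completed, H0 not rejected | Sum of the two | Printed non-efficacy |
|---|---|---|---|---|---|
| 0% | 2.6 (2.4) | 76.6 | 16.4 | 93.0 | 92.7 |
| 10% | 7.6 (7.8) | 59.9 | 30.3 | 90.2 | 89.6 |
| 20% | 18.7 (19.0) | 37.1 | 43.2 | 80.3 | 79.8 |
| 30% | 38.5 (38.6) | 16.3 | 44.9 | 61.2 | 61.0 |
| 40% | 62.9 (62.9) | 5.1 | 31.9 | 37.0 | 37.0 |
| 50% | 83.9 (84.2) | 0.8 | 15.2 | 16.0 | 15.8 |
| 60% | 95.9 (96.0) | 0.1 | 4.0 | 4.1 | 4.0 |

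Simulated harm at PE 0% is 4.4 (printed 4.9). At HR 1.5 interim non-efficacy is 68.4 (printed 66.0), so there the column is close to a true interim probability. Final-analysis CIs lying below 40% account for only 0–0.7 points of the completed group.

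**5. Sensitivity to the trigger.** I varied the start from the first DSMB meeting to the 67th infection, with 6-monthly looks and 2,000–5,000 trials per cell. Interim non-efficacy was 76–83 at PE 0%, 35–41 at 20%, 15–21 at 30%, 4.0–7.7 at 40%, 0.3–2.0 at 50% and 0–0.7 at 60%. A separate variant with the first look at the 20th infection gave 8.4 at PE 40%. At PE 40%, dropping the lower-limit clause, dropping the 150-at-risk rule, dropping dose stratification or adding an 8-week data lag gave 4.7–5.2, and 13-weekly looks gave 5.9. The most extreme setting, 4-weekly looks from 10 infections, gave 88, 52, 31, 14, 6.3 and 1.8 at PE 0, 20, 30, 40, 50 and 60%. All are below the printed values.

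**The case against.** Four points can be made for the table.

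- **The error rates are intact.** The false-positive and false-negative trade-off in Section 4.6.1 rests on the power column, which already includes the monitoring. Section 2.4.5 cites Table 4-2 only for the low risk of stopping for harm. This stands: no error rate is wrong. But how often the rule stops a trial early is itself one of the reported operating characteristics, and it is misstated.
- **It is a labelling matter.** The rows partition all outcomes, and the residual class was placed under non-efficacy. That is probably how the column arose. The label still says interim and PE < 40%, and nothing tells the reader otherwise.
- **The rule may be wider than the CI.** Table 4-6 says the boundary is supplemented with conditional power, as specified in the monitoring plan. Section 4.6.1 lists the CI rule alone as the simulation assumption, and neither document gives a conditional-power stopping threshold. The 20% bound is therefore conditional on the CI rule and on 6-monthly looks.
- **The simulated trigger is unknown.** This also stands, and the replacement values are a range for that reason. No start I tried matches every column as an interim outcome. With a start at 45 or more infections, the high-efficacy cells at PE 90% and 95% (85.4, 99.2) are reproduced only if final-analysis results are counted (86.5, 99.2; interim only 45.2, 28.6). Starts at 20–30 infections come close at interim, but give harm of 2.0–3.4 at PE 0% (printed 4.9).

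Figure 4-3 could not be seen. It is implicated only because the text says that it carries the same information.

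**Conclusion.** The concern holds. For true PE from 0% to about 60%, the non-efficacy column is the probability of not stopping for harm and not rejecting the null. It is not the probability of an interim non-efficacy stop. The overstatement is about 16 points at PE 0% (92.7 − 76.6), 43 at 20%, 45 at 30%, 32 at 40%, 15 at 50% and 4 at 60%. These sizes assume the CI-only rule, 6-monthly looks, the Section 4.6.1 incidence, dropout and accrual, and the SAP trigger of 45–67 infections. The direction does not depend on the trigger. For effective products the error is on the cautious side; for an ineffective product it makes early stopping look more likely than it is.

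**What to change.** - From the sponsor's own simulation output and actual trigger, restrict the Non-Efficacy column to trials that meet the CI rule at an interim look.
- Add a column for trials completed without rejecting H0, split by whether the final CI excludes 40%.
- At minimum, relabel the existing column as stopped for non-efficacy or H0 not rejected.
- Check Figure 4-3 and correct it in the same way if it plots the same quantity.
- State under the table which start trigger was simulated and whether the High Efficacy column counts final-analysis results. The timing matters: SAP Section 9.2.4 notes that, with a strict start at the 67th infection, there might be no interim non-efficacy analysis at all, and "Moreover, a high efficacy analysis would not occur, as its timing is synchronized to the non-efficacy monitoring timing".

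The cost is a re-tabulation of existing output, or one changed label. Nothing in the design changes, but the stated chance of stopping an ineffective product early becomes less favourable.
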